
the investigator will obtain the following information, as available:
 
 
• investigational center number and principal investigator name
 
• name, phone number, and address of the source of the complaint
 
• clinical protocol number
 
• patient identifier (patient study number) and corresponding visit numbers, if applicable
 
• product name and strength for open-label studies
 
• patient number, bottle, and kit numbers (if applicable) for double-blind or open-label studies
 
• product available for return Yes/No
 
• product was taken or used according to protocol Yes/No
 
• description or nature of complaint
 
• associated serious adverse event Yes/No
 
• clinical supplies unblinded (for blinded studies) Yes/No
 
• date and name of person receiving the complaint
 
 
Note: Reporting a complaint must not be delayed because not all the required information can be immediately obtained. Known information must be immediately reported. The sponsor will collaborate with the investigator to obtain any outstanding information.
 
11.4.2 Handling the Study Drug at the Investigational Center
 
The investigator is responsible for retaining the product in question in a location separate from the investigator's clinical study supplies. The sponsor may request that the investigator return the product for further evaluation and/or analysis. If this is necessary, the clinical study monitor or designee will provide the information needed for returning the study drug.
 
If it is determined that the investigational center must return all of the study drug, the sponsor will provide the information needed to handle the return.
 
The integrity of the randomization code and corresponding blinded clinical supplies will be maintained whenever possible. A serious
		

Original text with changes shown	New wording	Reason/Justification for change

adverse event or the potential for a product quality problem existing beyond the scope of the complaint may be a reason to unblind the clinical supplies for an affected patient.
		

114.3 Adverse Events or Serious Adverse Events Associated with a Product Complaint
 
If there is an adverse event or serious adverse event, the protocol should be followed.
		

11.4.4 Documenting a Product Complaint
 
The investigator will record a description of the product complaint in the source documentation as well as any actions taken to resolve the complaint and to preserve the safety of the patient. Once the complaint has been investigated by the sponsor and the investigator, if necessary, an event closure letter may be sent to the investigational center where the complaint originated or to all investigational centers using the product.
		

12.1. Informed Consent
 
Overall, this study includes: (I) an informed consent for the clinical study (main study) and (II) informed consent forms for the ancillary studies (CSF and OCT), and (III) informed consent forms for dummy run scans (MRI and OCT) required prior to initiation of the study and ancillary study respectively.
	
Overall, this study includes: (I) an informed consent for the clinical study (main study), (II) informed consent forms for the ancillary studies (CSF and OCT), and (III) informed consent forms for dummy run scans (MRI and OCT) required prior to initiation of the study and ancillary study respectively.
	
For completeness, dummy run informed consent added to this section

APPENDIX B. GUIDANCE ON SAFETY MONITORING
		

a. b. If the blood test is negative, the <del>subject patient</del> will be contacted and informed about the test result and the study drugs will be <del>sent to her by courier</del> dispensed as soon as possible.
	
b. If the blood test is negative, the patient will be contacted and informed about the test result and the study drugs will be dispensed as soon as possible.
	
It has been clarified that it is not acceptable to courier study drug to the patient in this manner

12. 5. Guidance on monitoring patients with elevated pancreatic amylase levels
 
Pancreatic amylase will be measured at each study visit. Lipase will be tested in case of abnormal pancreatic amylase results. In case of suspected pancreatitis, the patient should undergo a thorough clinical evaluation including an abdominal CT scan as soon as possible in order to clarify the diagnosis and enable assessment of severity of this condition.
	
(new text)
	
Subsection added for consistency with other laquinimod protocols and on the advice of the Data Monitoring Committee

APPENDIX C. MODERATE/STRONG CYP3A4 INHIBITORS AND CYP3A4 INDUCERS
		

(additional CYP3A4 inhibitors added to the medication classes
	
(see Appendix C for revised section)
	
Section updated in accordance

Original text with changes shown	New wording	Reason/Justification for change
antivirals [danoprevir, ledipasvir, elvitegravir] and antiemetics [casopitant, netupitant], and medication class antiarrhythmics [dronedarone] added.  List of CYP3A4 inducers replaced with table)		with Investigator's Brochure
APPENDIX E. CYP3A4 and CYP1A2 substrates  (original protocol text replaced by table)	(see Appendix E for revised section)	Section updated in accordance with Investigator's Brochure
APPENDIX J. MODIFIED RANKIN SCALE  (new appendix)	(see Appendix J)	Appendix added to document the efficacy measure that has been added to the study
APPENDIX L. OCT ANCILLARY STUDY DESIGN AND METHODOLOGY  The following criteria lead to exclusion of affected eyes only. However, the patient can participate in the OCT ancillary study with a single eye, if it is unaffected.	(new text)	Clarification that only affected eyes are excluded from the OCT assessments, such that patients with an unaffected eye can participate for that eye only
(in Table 10, the following changes have been made: 
 
title amended to add 'of affected eyes'
 
more than 4 diopters (instead of more than 6 diopters) of myopia or hyperopia will exclude an eye
 
correction of error, should be 'systemic lupus erythematosus', not 'systemic lupus erythematoses'
 
footnote added for selected categories, 'Indicates conditions which are likely to affect both eyes and therefore lead to exclusion of the patient, even if 1 eye is considered unaffected')
 
 )	(see Appendix L for revised table)	Corrections and clarifications

## **APPENDIX A. RELAPSE DEFINITION**

### **Relapse (attack)**

A relapse will be defined as the appearance of 1 or more new neurological abnormalities or reappearance or worsening of 1 or more previously observed neurological abnormalities. This change in clinical state must last at least 48 hours and be immediately preceded by an improving neurological state of at least thirty (30) days from onset of previous relapse.

This criterion is different from the clinical definition of relapse: "at least 24 hours duration of symptoms." Since "in study" relapse definition must be supported by an objective neurological evaluation (see next paragraph), a neurological deficit must be sustained long enough to eliminate pseudo-relapses.

An event is counted as a relapse only when the patient's symptoms are accompanied by observed objective neurological changes. A change in bowel/bladder function or in cognitive function must not be entirely responsible for the changes.

The patient must not be undergoing any acute metabolic changes such as fever or other medical abnormality.

### **Relapse Evaluation Procedures**

Patients will be instructed to telephone their study site within 48 hours should any symptoms suggestive of a relapse appear.

The Treating Neurologist will evaluate the patient once any symptom suggestive of a relapse occurs.

In case of a suggestive relapse during a scheduled or unscheduled visit, the Treating Neurologist will refer the patient to the Examining Neurologist.

The Examining Neurologist will evaluate the patient within 7 days of symptoms onset, conditional upon a symptomatic period of  $\geq 48$  hours.

### Patient Evaluation by the Examining Neurologist

EDSS and FSS will be administered.

### Clinical Relapse Determination by the Treating Neurologist

The determination whether objective neurological changes are present consistent with a relapse will be made by the Treating Neurologist, without reference to the EDSS and FSS administered by the Examining Neurologist.

Follow-up visits to monitor the course of the relapse will be made at the Treating Neurologist's discretion.

### **Protocol-Defined Relapse**

In addition to the criteria used by the Treating Neurologist to determine that a clinical relapse has occurred, a per-protocol relapse definition will make use of EDSS data to confirm that the objective neurological changes include at least 1 of the following:

- an increase of at least 0.5 in the EDSS score as compared to previous evaluation

Placebo-Controlled Study – Multiple Sclerosis  
Clinical Study Protocol with Global Amendment 02 Study TV5600-CNS-20006 (ARPEGGIO)

- an increase of 1 grade in the score of 2 or more of the 7 functions from the FSS as compared to previous evaluation
- an increase of 2 grades in the score of 1 function from the FSS as compared to the previous evaluation

## APPENDIX B. GUIDANCE ON SAFETY MONITORING

### 1. Guidance on Monitoring Patients with Elevated Liver Function Tests

Liver enzymes (ALT, AST, GGT, ALP), as well as direct and total bilirubin will be measured at each study visit.

In any case of elevated ALT or AST to a level exceeding of  $\geq 2 \times$ ULN (including patients whose baseline ALT or AST levels are  $\geq 2 \times$  and  $\leq 3 \times$  the ULN, who may be enrolled in the study), a thorough medical history and physical examination with a focus on liver disease should be undertakena. In addition, the patient should be instructed to refrain from alcoholic beverages.

In case of symptoms compatible with drug-induced liver injury, the patient should be invited for an unscheduled visit to measure liver enzymes as soon as possible.

Solitary elevations of total bilirubin, not accompanied by elevations of ALT or AST should be managed according to the discretion of the Treating Neurologist.

#### 1.1. Elevation of Either ALT or AST to $\geq 3 \times$ ULN:

Confirmation of the abnormality (in case the abnormality is of ALT or AST  $\geq 8 \times$ ULN, no confirmation is required prior to study drug discontinuation, but the assessments below should be performed):

- The day in which the abnormal value is received from the laboratory will be considered as Day 0.
- The Investigator should repeat the test before Day 2, for confirmation purposes (this may be performed in a local laboratory along with CBC and differential to assess for eosinophilia. In general, in case a blood sample is sent to a local laboratory, the following assessments [and reference ranges] are mandatory: ALT [serum glutamic pyruvic transaminase; SGPT], AST [serum glutamic oxaloacetic transaminase; SGOT], ALP, total bilirubin, CBC [with differential for eosinophil count, separate tube], and INR [separate tube; not to be sent in a confirmatory test]). The investigator should also question the patient regarding symptoms.

The abnormality will be regarded as confirmed in each of the following scenarios:

1. In case baseline value was within normal range and ALT or AST is still  $\geq 3 \times$ ULN
2. In case baseline value was above ULN and ALT or AST is  $\geq 2 \times$  the baseline value.

Upon confirmation of the abnormality as noted above, the following additional evaluations should be performed and results should be recorded in the CRF.

---

a Thorough medical history with a focus on liver disease: Personal or family history of liver disease; personal history of a systemic disease with potential liver involvement; exposure to alcohol, medications (prescription or OTC), herbal preparations, dietary supplements, recreational drugs, special diets or environmental chemical agents; potential exposure to infectious agents (eg, travel to developing countries, history of potential exposure to blood or blood products, high-risk sexual relations) and any additional information deemed relevant by the investigator. Physical examination – including signs of chronic liver disease

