### **Additional Tests/Evaluations**

- Serology for Hepatitis A (antibody, immunoglobulin M and G), B (core antibody total, core immunoglobulin M, and surface antigen), and C viruses (central laboratory).
- Serology for autoimmune hepatitis: anti-nuclear antibodies (titer), Anti Smooth Muscle Antibodies (ASMA), anti-Liver Kidney Microsomal (LKM) antibodies (central laboratory). Further testing may be required in case of a positive result for Hepatitis B or C.
- An ultrasound examination of the liver and biliary tract.
- Other diagnostic tests/consultations, as deemed necessary by the investigator, eg, serology for hepatitis E virus in case of travel to endemic geography

Observation and Follow-Up (to be performed after the abnormality was confirmed as above)

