#### **1.1.1. ALT or AST $\geq 3 \times$ and $\leq 5 \times$ ULN (if baseline value is $\geq 2.5 \times$ ULN, ALT or AST $\geq 3.5 \times$ ULN and $\leq 5 \times$ ULN)**

In addition to the above procedures required for any elevation to levels  $> 3 \times$ ULN:

- ALT, AST, GGT, ALP, total and direct bilirubin, CBC and differential (to assess for eosinophilia) and INR should be monitored on days 5 ( $\pm 2$ ), 8 ( $\pm 2$ ), 14 ( $\pm 2$ ), and 28 ( $\pm 2$ ). On at least 1 of these days, the test should be performed centrally. (INR should be sent to a local laboratory only.)
- In cases where a local laboratory is used, the results should be recorded in the CRF, accompanied by the reference range of the relevant measurements.
- Should the abnormality (ALT or AST  $\geq 3 \times$  and  $\leq 5 \times$ ULN [if baseline value is  $\geq 2.5 \times$ ULN, ALT or AST  $\geq 3.5 \times$ ULN and  $\leq 5 \times$ ULN]) persist further, the patient will be followed according to the investigator's discretion, but at least once a month a blood sample for ALT, AST, GGT, ALP, and total and direct bilirubin should be sent to the central laboratory.

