#### **1.1.2. ALT or AST $\geq 5 \times$ but less than $8 \times$ ULN**

In addition to the above procedures required for any elevation to levels  $> 3 \times$ ULN:

- ALT, AST, GGT, ALP, total and direct bilirubin, CBC and differential count (to assess for eosinophilia), and INR should be monitored twice a week.
- At least for every other measurement, the tests should be sent to the central laboratory. The rest of the tests may be sent to a local laboratory. INR should always be sent to a local laboratory.

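### Draw a local INR with the repeat liver test: Appendix B leaves it out, so the INR criterion for stopping drug cannot be read from the one prompt sample (minor, patient safety)

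*Protocol*

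**What the plan says.** Three places in the Protocol act on the same combination. Section 3.6.2 (Liver Enzymes) and Appendix B 1.2 (Stopping Rules) call for immediate discontinuation at any rise in ALT or AST to at least 3×ULN with INR above 1.5 or total bilirubin above 2×ULN. Section 7.1.1 requires immediate cessation and a serious adverse event report for essentially the same picture. None of the three mentions confirmation or baseline.

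Section 7.3.1 makes coagulation testing conditional on Appendix B, so INR is not measured routinely. Appendix B 1.1 then sets the sequence:

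- The day the abnormal value is received is Day 0. "The Investigator should repeat the test before Day 2, for confirmation purposes".
- For local samples, "In general, in case a blood sample is sent to a local laboratory, the following assessments [and reference ranges] are mandatory". INR is on that list, but with the qualifier "INR [separate tube; not to be sent in a confirmatory test".
- With a normal baseline, the abnormality is confirmed if the repeat is still at least 3×ULN. The other scenario, beginning "In case baseline value was above ULN and ALT or AST is", requires at least twice the baseline value.
- The follow-up block is headed "Observation and Follow-Up (to be performed after the abnormality was confirmed as above". Within it, 1.1.1 (3–5×ULN) says "CBC and differential (to assess for eosinophilia) and INR should be monitored on days 5" (±2), 8, 14 and 28, and 1.1.2 (5 to below 8×ULN) says "and INR should be monitored twice a week".
- At 8×ULN or more, 1.1 waives confirmation before drug is stopped.

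**The concern.** A stopping criterion is useful only if the test behind it is available when the decision is due. Bilirubin is measured at each visit and is on the list for a local repeat, but INR is withheld from that repeat and appears only after confirmation.

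The patient at stake has ALT or AST of 3 to below 8×ULN, INR above 1.5, total bilirubin below 2×ULN, and none of the listed symptoms or eosinophilia. The protocol intends this patient to stop drug and be reported as a serious adverse event. Unless the investigator orders an INR on their own initiative, daily dosing continues and the report is not triggered until the first scheduled INR. For some patients with a raised baseline there is no scheduled INR at all.

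Nothing here touches the primary endpoint, power or alpha.

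**Working it through.** The plan gives no figure to reproduce, so the check is of dates, thresholds and the number of patients entering the pathway.

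**1. Delay at 3–5×ULN.** Inputs: repeat before Day 2, so Day 0 or 1 (Appendix B 1.1); first INR on Day 5 ± 2, so Day 3 to 7 (1.1.1).

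- Shortest gap: 3 − 1 = 2 days. Longest gap: 7 − 0 = 7 days.
- At one dose a day, that is 2–7 further doses. This compares draw dates and assumes the same laboratory turnaround for both samples.
- At 5 to below 8×ULN the frequency is given but no start day, so no gap can be calculated.

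**2. Raised baseline.** Confirmation needs at least 2 × baseline, while the stopping rules start at 3×ULN. The range with no scheduled INR therefore runs from 3×ULN to just below 2 × baseline, and exists only when baseline exceeds 3/2 = 1.5×ULN.

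| Baseline (×ULN) | 2 × baseline (×ULN) | Repeat values with no scheduled INR (×ULN) |
|---|---|---|
| 1.5 | 3.0 | none |
| 1.6 | 3.2 | 3.0 to <3.2 |
| 2.0 | 4.0 | 3.0 to <4.0 |
| 2.5 | 5.0 | 3.0 to <5.0 |

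Exclusion criterion 22 removes patients at 3×ULN or more at screening, but Appendix B 1 says that patients with baselines from 2×ULN may be enrolled, so these rows are not hypothetical.

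**3. Patients entering the pathway.** Inputs: Table 4 (peak values in patients with normal baselines, ALLEGRO and BRAVO) and 140 per arm (SAP Section 3.3).

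- ALT >3 to 5×ULN: 140 × 30/888 = 4.7 on laquinimod and 140 × 5/930 = 0.8 on placebo, together 5.5.
- ALT >5 to 8×ULN: 140 × 5/888 = 0.8 and 140 × 6/930 = 0.9, together 1.7.
- ALT total: 5.5 + 1.7 = 7.2.
- AST >3 to 8×ULN: 140 × 10/950 + 140 × 10/977 = 1.5 + 1.4 = 2.9.
- Range: 7.2 if every AST case is also an ALT case, 7.2 + 2.9 = 10.1 if none is. That is about 7–10 of 280.

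These are peaks over up to 2 years in relapsing-remitting disease, and rates from normal-baseline patients are applied to everyone. They say nothing about the raised-baseline range, and they count everyone entering the pathway, not those with an isolated INR rise.

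**The case against.** The strongest reply is that confirming first is deliberate. Appendix B 1.1 waives confirmation before discontinuation at 8×ULN or more, a waiver with little purpose unless lower elevations are normally confirmed before stopping. Section 3.6.2 sends the site to Appendix B from 2×ULN upward, and the stopping rules follow the confirmation step there. An order to stop immediately also governs what happens once a criterion is known to be met; it sets no deadline for obtaining the INR. And the exclusion is written out explicitly, so it looks like a choice.

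Much of this stands. A reader might infer that the protocol flatly contradicts itself because no confirmation is required below 8×ULN. The documents do not support that: the three stopping provisions state no such condition, but the waiver suggests one. On the confirm-first reading, an unconfirmed value in the raised-baseline range may not be meant to trigger the INR criterion at all. That reading does not explain why the INR must wait until Day 3–7 once the repeat has confirmed the rise.

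Existing safeguards also count. Bilirubin, symptoms and eosinophilia can be judged at the repeat, drug stops outright at 8×ULN, and Section 3.11.6 lets the Treating Neurologist add procedures for safety. The urgent panel in Section 7.3.4 does not itself name INR. Discretion is an incomplete answer, because a site following the written instruction will leave the INR out.

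**Conclusion.** The point holds as a minor, inexpensive improvement in patient safety. On either reading of the confirmation step, the INR criterion cannot be judged from the repeat sample. The consequence is a 2–7 day wait at 3–5×ULN, an undefined wait at 5 to below 8×ULN, and no scheduled INR for baselines above 1.5×ULN when the repeat falls between 3×ULN and twice baseline.

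The number of patients who would have an isolated INR above 1.5 is not given and is probably very small. Section 1.4.1 reports that Hy's law criteria were not met and that there were no cases of liver failure. A reader might take the 7–10 of 280 as patients at risk from the omission; that would be wrong. It is the number likely to enter the pathway, so it measures what the fix costs. It rests on Table 4 carrying over to this population and follow-up.

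**What to change.** In Appendix B 1.1, delete the part of the INR bracket after the semicolon and add: a local INR in a separate tube is drawn with the repeat sample for any ALT or AST of at least 3×ULN, whatever the baseline value and whichever laboratory runs the repeat chemistry.

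This makes the INR criterion readable from a sample taken before Day 2 for normal and raised baselines alike. Confirmation thresholds, serology, ultrasound and the follow-up schedule stay as they are.

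The cost is one wording edit and one extra local tube per repeat, for roughly 7–10 of 280 patients plus any with raised baselines who reach 3×ULN. No new laboratory arrangement is needed, since 1.1.1 already says "INR should be sent to a local laboratory only".

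A separate drafting point should be clarified at the same time: for baselines of 2.5×ULN or more, 1.1.1 starts its tier at 3.5×ULN, whereas 1.1 confirms only at twice baseline, which is at least 5.0×ULN. The sponsor should state which threshold governs. The INR edit does not settle that, and the point above does not depend on it.

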## **1.2. Stopping Rules:**

In the following circumstances, the study drug will be discontinued immediately:

- Any increase in ALT or AST to  $\geq 3 \times \text{ULN}$ , combined with INR  $> 1.5$  or total bilirubin  $> 2 \times \text{ULN}$
- Any increase in ALT or AST to  $\geq 3 \times \text{ULN}$ , which is accompanied by nausea, vomiting, fever, rash, or eosinophilia
- Any increase in ALT or AST to levels  $\geq 5 \times$  but  $< 8 \times \text{ULN}$ , which is persistent for  $\geq 2$  weeks of repeated measurements
- Any increase in ALT or AST to levels  $\geq 8 \times \text{ULN}$
- In any case where monitoring of liver enzymes cannot be performed according to the protocol guidance

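### For an isolated rise in an enzyme with baseline 2.5 to <3 × ULN, the confirmation rule in Appendix B 1.1 blocks first entry to the 3.5–5 × ULN follow-up tier that 1.1.1 sets for these patients

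*Protocol*

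**What the plan says.** Protocol Appendix B section 1.1 asks for a repeat test after ALT or AST reaches 3 × ULN and gives two ways in which the abnormality counts as confirmed:

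- Normal baseline: "In case baseline value was within normal range and ALT or AST is still" at least 3 × ULN.
- Raised baseline: "In case baseline value was above ULN and ALT or AST is" at least twice the baseline value.

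Everything further depends on confirmation. The work-up (hepatitis and autoimmune serology, liver ultrasound) is introduced by "Upon confirmation of the abnormality as noted above, the following additional evaluations should be performed", and the follow-up heading says "to be performed after the abnormality was confirmed as above".

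Section 1.1.1 then sets a tier of 3 to 5 × ULN, with its own floor of 3.5 × ULN for patients whose baseline is 2.5 × ULN or more. It schedules tests around days 5, 8, 14 and 28. If the abnormality persists, "at least once a month a blood sample for ALT, AST, GGT, ALP, and total and direct bilirubin should be sent to the central laboratory". Section 1.1.2 covers 5 to below 8 × ULN, where enzymes, bilirubin, blood count "and INR should be monitored twice a week".

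The opening of Appendix B section 1 expects patients with baselines of 2 to 3 × ULN to be enrolled. Exclusion criterion 22 (Protocol 4.2) removes only screening values of 3 × ULN or more.

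**The concern.** The two sections use different yardsticks for the same patients. Section 1.1 measures the rise against the patient's own baseline. Section 1.1.1 measures it against ULN, with a floor written for baselines of 2.5 × ULN or more. At those baselines, doubling takes the value to the top of the tier or beyond, so the tier cannot be entered on a first rise in that enzyme.

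At stake is scheduled liver monitoring: the tests on days 5, 8, 14 and 28 with monthly tests after that, the serology, and the ultrasound. Just above 5 × ULN the twice-weekly schedule is lost too. That schedule supplies the repeated measurements for the rule in section 1.2 that stops drug when 5 to below 8 × ULN persists for two weeks.

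**Working it through.** **Inputs.** Write b for baseline and v for the repeat value, both in multiples of ULN.

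- Confirmation for b > 1: v ≥ 2b (Appendix B 1.1).
- Tier 1.1.1 for b ≥ 2.5: 3.5 ≤ v ≤ 5. For lower b: 3 ≤ v ≤ 5.
- Tier 1.1.2: 5 ≤ v < 8.
- Range of b of interest: 2.5 to <3 (tier floor in 1.1.1, exclusion criterion 22).

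The plan derives no figure here. Its stated tier of 3.5 to 5 is what is tested.

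**Can a value in the tier be confirmed?** It needs 2b ≤ v ≤ 5, so b ≤ 2.5. Together with b ≥ 2.5 this leaves the single point b = 2.5, v = 5.0, which also falls in 1.1.2.

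| b | Confirmed at (2b) | No scheduled intensified follow-up | Part of 1.1.2 missed (5 to <2b) |
|---|---|---|---|
| 2.5 | 5.0 | 3.5 to <5.0 | none |
| 2.6 | 5.2 | 3.5 to <5.2 | 5.0 to <5.2 |
| 2.7 | 5.4 | 3.5 to <5.4 | 5.0 to <5.4 |
| 2.8 | 5.6 | 3.5 to <5.6 | 5.0 to <5.6 |
| 2.9 | 5.8 | 3.5 to <5.8 | 5.0 to <5.8 |

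Below b = 2.5 the tier is only partly closed. At b = 2.0, values of 4.0 to 5.0 can be confirmed, and at b = 2.4, values of 4.8 to 5.0. Up to b = 1.5 the whole 3 to 5 tier is open.

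**Tests lost before the next visit.** Visits fall at weeks 4, 8 and 12, then every 12 weeks (Protocol 3.11.3). Suppose the rise is found at a scheduled visit. With 4 weeks to the next one, three tests are lost (days 5, 8, 14). With 12 weeks, at least five are lost (days 5, 8, 14, 28 and one monthly).

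**Group size.** The documents do not give the share of patients with b ≥ 2.5. A loose ceiling comes from the pivotal RRMS studies: 983 patients took 0.6 mg (Protocol 1.4.1), of whom 888 had normal baseline ALT and 950 normal baseline AST (Protocol Table 4).

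- ALT not normal or missing: (983 − 888)/983 = 95/983 = 9.7%.
- AST not normal or missing: (983 − 950)/983 = 33/983 = 3.4%.

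If those shares held among the 280 patients planned for 0.6 mg and placebo, which is an assumption, the ceilings would be 27.1 and 9.4 patients with any non-normal or missing value. Those at 2.5 or more are a fraction of that.

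**The case against.** **The tier is still in use.** This stands. A patient confirmed at 5 × ULN or more can step down into 3.5–5 × ULN, where the wording on persistence in 1.1.1 applies. The other enzyme can also confirm the abnormality under its own baseline, for example AST normal at baseline and still at 3 × ULN or more. A reader might infer that the 3.5 × ULN wording is dead text. It is not. Only first entry on an isolated rise is blocked.

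**Patients are not left unmonitored.** This also stands. Still in force are:

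- enzymes at every visit, the history and examination at 2 × ULN, and the repeat test;
- symptom-triggered visits (Appendix B 1) and discretionary tests (Protocol 3.11.6, 7.3.4);
- monitoring of adverse events at suitable intervals (Protocol 7.1.1, 7.1.2);
- the stopping rules, none of which requires confirmation under 1.1.

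A site applying the two-week rule at 5.2 × ULN would have to re-measure. But none of these fixes the test days, the serology or the ultrasound.

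**INR.** A reader might infer that this gap disables the stopping limb for ALT or AST of at least 3 × ULN "combined with INR" above 1.5. The documents do not support that. INR is "not to be sent in a confirmatory test" for any patient, whatever the baseline. The alternative bilirubin limb is covered at each visit and in any local repeat sample.

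**Table 4.** A reader might infer that the blocked range is where the drug's main ALT effect lies. Table 4 covers only patients with normal baselines, and its largest excess is lower, at >1 to ≤3 × ULN: 29.5% on 0.6 mg against 17.7% on placebo. At >3 to ≤5 × ULN it is 3.4% (30/888) against 0.5% (5/930). Above 5 × ULN there is none: 10/888 (1.1%) against 13/930 (1.4%). This is indirect context at most.

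**Wider intent.** Sections 1.1.1 and 1.1.2 refer to procedures for any elevation above 3 × ULN, so some sites may follow the tier regardless. That does not resolve the conflict with the explicit condition in the follow-up heading. It means that sites may differ.

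**Conclusion.** The rule is wrong as written. For an isolated first rise from a baseline of 2.5 to <3 × ULN, confirmation needs 5.0 to <6.0 × ULN. The 3.5–5 × ULN tier is therefore closed except at one boundary point, and part of 1.1.2 is delayed. This follows from the protocol text and needs no outside assumption.

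The consequence is a minor patient-safety issue. An affected patient needs a high baseline in one enzyme, no confirming rise in the other, and a value between 3.5 × ULN and twice baseline. The number of such patients is unknown and may be zero. The ceilings of about 27 (ALT) and 9 (AST) rest on carrying RRMS baselines over to this trial, and they count every non-normal or missing value. No endpoint or analysis is affected.

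**What to change.** Amend the second scenario in Appendix B 1.1: for a baseline above ULN, the abnormality is confirmed when the repeat ALT or AST is at or above the lower of 2 × baseline and 3.5 × ULN.

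| b | Current threshold | Proposed threshold |
|---|---|---|
| 1.2 | 2.4 | 2.4 |
| 1.75 | 3.5 | 3.5 |
| 2.0 | 4.0 | 3.5 |
| 2.4 | 4.8 | 3.5 |
| 2.5 | 5.0 | 3.5 |
| 2.9 | 5.8 | 3.5 |

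Baselines up to 1.75 × ULN are unchanged. Above that, the threshold is lower. The 3.5–5 tier opens, and every repeat value of 5 × ULN or more is confirmed. The change reaches below 2.5 on purpose: applied only from 2.5 upward, the threshold would drop from 4.8 at baseline 2.4 to 3.5 at 2.5. For baselines of 1.75 to <2.5, values of 3.0 to <3.5 × ULN stay unconfirmed, a residual gap that the change narrows but does not close. Deleting the 3.5 × ULN wording from 1.1.1 instead would not help values from 5 × ULN to below twice baseline.

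The cost is a few extra blood tests, serologies and ultrasounds. At baseline 2.9, confirmation would follow a 21% rise (3.5/2.9 = 1.21), but 3.5 × ULN is the sponsor's own floor. Because it adds procedures, the change probably needs a written amendment with ethics approval (Protocol 11.1.1) rather than a clarification. Sample size and analysis are untouched.
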